6.1 Study treatment

For this study, the investigational drugs are MCS110, an anti-CSF-1 recombinant humanized monoclonal antibody, and PDR001, an anti-PD-1 receptor recombinant humanized monoclonal antibody. The study treatment is the combination of MCS110 and PDR001, or single agent MCS110 or PDR001 if one of the investigational drug need to be discontinued.

6.1.1 Dosing regimen

Table 6-1 Dose and treatment schedule

Study treatments	Pharmaceutical form and route of administration	Dose	Frequency and/or Regimen
MCS110	Liquid concentrate in vial i.v. infusion	3 mg/kg (starting dose)	Every 3 weeks
PDR001	Powder for solution for infusion	100 mg (starting dose)	Every 3 weeks

MCS110 and PDR001 will be administered once every 3 weeks via i.v. infusions over 1 hour and 30 minutes, respectively. The drugs will be administered separately with at least a 30 min break between the two antibodies. Infusions of each antibody can be extended to up to 2 hours if clinically indicated.

Both study drugs may be infused using the same i.v. access site. The same administration sequence must be followed for all patients, i.e. PDR001 should be infused first. If an infusion reaction occurs after administration of PDR001, the subsequent MCS110 infusion must be delayed until it is safe for the patient to receive MCS110 based on the clinical discretion of the investigator. The delay between PDR001 and MCS110 infusions can be up to 4 hours if clinically indicated.

A scheduled dose of ongoing study drugs may be delayed by up to 7 days to recover from previous AEs or a missed visit (see [Section 6.3.2](#)). If a scheduled dose of ongoing study drugs is delayed longer than 7 days due to an unresolved AE, the administration should be skipped and treatment resumed at a lower dose level (if meeting criteria for DLT) at the next scheduled dose. The assessment schedule will be shifted accordingly. Dose delays refer to all ongoing study drugs: for combination treatment both MCS110 and PDR001 and for single agent treatment MCS110 or PDR001. Dose modifications should follow [Section 6.3.1](#) and [Section 6.3.2](#).

The dose for MCS110 study drug will be calculated from the individual subjects' body weight as measured at the screening visit and subsequent visits prior to the administration.

After Phase Ib part, if emerging PK, PD, and safety data indicate that a flat dosing strategy of MCS110 is appropriate, then a flat dosing strategy may be implemented in the Phase II part of the study. The PK data obtained during Phase Ib part of this study will be combined with PK data from the other MCS110 clinical studies to assess the flat dosing vs. body-weight based dosing, and a flat dose may be identified for the Phase II part of this study.

6.1.2 Ancillary treatments

Patients should not receive pre-medication to prevent infusion reactions before the first infusion of the study treatment, in order to determine if pre-medication is necessary. If a patient experiences an infusion reaction, he/she may receive pre-medication on subsequent dosing days. The pre-medication should be chosen per institutional standard of care at the discretion of the treating physician; however, steroids should be avoided if possible.

Acute allergic reactions should be treated as needed per institutional standard of care. In the event of anaphylactic/anaphylactoid reactions, this includes any therapy necessary to restore normal cardiopulmonary status. If a patient experiences a Grade 3 anaphylactic/anaphylactoid reaction, the patient may only continue on the study following discussion with Novartis.

Patients should be treated in a facility equipped for cardiopulmonary resuscitation. Appropriate resuscitation equipment should be available at the bedside and a physician readily available.

Guidelines on management of infusion reactions are provided in [Table 6-4](#).

The CTCAE category of “Infusion related reaction” should be used to describe infusion reactions, unless the investigator considers another category, such as “Allergic reaction,” “Anaphylaxis,” or “Cytokine release syndrome” more appropriate in a specific situation.

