Grade 2 myocarditis, or Grade ≥ 3 other cardiac disorders related to study treatment	Discontinue study treatment
Musculoskeletal	
Grade 2 or Grade 3	Hold study treatment. Consider resuming study treatment without dose modification upon resolution to ≤ Grade 1 with appropriate management.
Grade 4	Discontinue study treatment. In some cases, resuming study treatment may be considered after discussion with the Novartis Medical Monitor and consultation with a rheumatologist.

Toxicity	Dose Adjustment Rules*
Neurology	
Grade 1	Consider study treatment hold, particularly for clinical suspicion of Guillain-Barre syndrome, encephalitis, aseptic meningitis, transverse myelitis, or peripheral neuropathy.
Grade 2	Hold study treatment. In some cases, resuming study treatment may be considered after discussion with the Novartis Medical Monitor.
Grade 3 or Grade 4	Discontinue study treatment.
Infusion Reaction	
Grade 1	Decrease infusion rate until recovery
Grade 2	Stop infusion. Before restarting - administer oral pre-medication (e.g. 1000 mg of acetaminophen/paracetamol, 50-100 mg diphenhydramine hydrochloride or alternative antihistamine), within 60 minutes of restarting the infusion. Restart infusion at 50% of previous rate under continuous observation. Ensure that there is a minimum observation period of 1 hour prior to restarting the infusion(s). If the AE recurs at the reinitiated slow rate of infusion, and despite oral pre-medication, then discontinue patient from treatment.
Grade 3 or 4	Discontinue infusion immediately, and discontinue study treatment. Provide supplemental oxygen, fluids, and other resuscitative measures as needed. Monitor vital signs (e.g. blood pressure, pulse, respiration, and temperature) every 15 ± 5 minutes until resolution.
Other laboratory adverse events, not specified elsewhere in table and not included in the consensus guidelines	
Grade 3	Hold study treatment. Upon resolution to ≤ Grade 1, resume study treatment without dose modification.
Grade 4	Isolated Grade 4 electrolyte abnormalities not associated with clinical sequelae and corrected after appropriate management within 72 hours of their onset do not require discontinuation. In the case of Grade 4 electrolyte imbalances associated with clinical sequelae, or not resolved to ≤ Grade 1 within 72 hours despite appropriate management, discontinue study treatment.
Other non-laboratory adverse events, not specified elsewhere in table and not included in the consensus guidelines	

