Grade 2	Consider study treatment hold, at Investigator discretion. Upon resolution to ≤ Grade 1, resume study treatment without dose modification.
Grade 3	Hold study treatment. Upon resolution to ≤ Grade 1, resuming study treatment must be discussed with the Novartis Medical Monitor.
Grade 4	Discontinue from treatment.
*Delay: treatment may be delayed for 7 days due to AEs. If a scheduled dose of ongoing study drugs is delayed longer than 7 days due to an unresolved AE, the administration should be skipped and treatment resumed at a lower dose level (if meeting the criteria for DLT) at the next scheduled dose (Section 6.1.1). Treatment: refers to both study drugs, unless one has been discontinued.	

Toxicity	Dose Adjustment Rules*
**Note: If Grade 3 or 4 hyper-bilirubinemia is due to the indirect (non-conjugated) component only, and hemolysis as the etiology has been ruled out as per institutional guidelines (e.g., review of peripheral blood smear and haptoglobin determination), then delay study treatment until resolved \leq Grade 1, and resume study treatment at the discretion of the investigator.	
***Note: A CT scan or other imaging study to assess the pancreas, liver, and gallbladder must be performed within one week of the first occurrence of any \geq Grade 3 of amylase and/or lipase.	

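### A Grade 3 anaphylactic reaction to a study infusion falls under two stopping rules: Protocol 6.1.2 lets the patient continue after sponsor discussion, while Table 6-4 requires discontinuation, and nothing says which prevails.

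*Protocol*

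**What the plan says.** Protocol 6.1.2 (Ancillary treatments) does three things that bear on this point.

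- It sets a condition for Grade 3 anaphylaxis: "If a patient experiences a Grade 3 anaphylactic/anaphylactoid reaction, the patient may only continue on the study following discussion with Novartis".
- It refers the reader elsewhere for management: "Guidelines on management of infusion reactions are provided in" Table 6-4.
- It makes 'Infusion related reaction' the default CTCAE category for describing an infusion reaction, "unless the investigator considers another category" more suitable. The examples given are allergic reaction, anaphylaxis and cytokine release syndrome.

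Table 6-4 (in Protocol 6.3.1) has an Infusion Reaction row. Its Grade 3 or 4 entry reads: "Discontinue infusion immediately, and discontinue study treatment". No route through sponsor discussion is offered. The table's footnote widens the effect: "Treatment: refers to both study drugs, unless one has been discontinued".

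Section 6.1.1 adds a general pointer, "Dose modifications should follow" Sections 6.3.1 and 6.3.2, but does not address the anaphylaxis sentence.

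**The concern.** A stopping rule for a severe reaction to an infused antibody should give one answer for one event. Here a Grade 3 anaphylactic reaction during a study infusion is covered by a rule that ends both drugs and by a sentence under which dosing may go on after a conversation with the sponsor. Two sites facing the same event could act differently, and each could cite the protocol.

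At stake is re-exposure after a severe reaction to the study antibodies themselves. The protocol treats this type of risk as serious: exclusion criterion 2 in Section 5.3 keeps out patients with a past severe hypersensitivity to another antibody. There is also a compliance question. Section 12 allows no authorised deviations and tells investigators not to ask the sponsor for one. If Table 6-4 controls, resuming after a sponsor discussion is a deviation. If 6.1.2 controls, it is compliant. No endpoint, sample size or analysis is affected.

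**Working it through.** The core of the check is a comparison of texts.

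**Step 1. Is it the same event?** Section 6.1.2 lists anaphylaxis among the categories that may describe an infusion reaction. A Grade 3 anaphylactic reaction to a study infusion is therefore an infusion reaction by the protocol's own usage, and it is also the event named in the Grade 3 sentence.

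**Step 2. What does each text require?**

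| Event | Source | Consequence |
|---|---|---|
| Grade 3 anaphylactic/anaphylactoid reaction | 6.1.2 | May continue, only after sponsor discussion |
| Grade 3 infusion reaction | Table 6-4, Infusion Reaction | Discontinue study treatment |
| Grade 4 infusion reaction | Table 6-4, Infusion Reaction | Discontinue study treatment |
| Grade 3 cytokine release syndrome | Table 6-4, own row | Discontinue study treatment |

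The conflict is confined to Grade 3, because the 6.1.2 sentence names only that grade.

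**Step 3. Does continuing on the study mean continued dosing?** Section 7.1.3 already keeps patients who stop treatment on the study, so no sponsor discussion would be needed for follow-up alone. Section 6.3.1 itself speaks of discontinuing a patient from the study when it means stopping treatment after repeated skipped doses. Continued dosing is the natural reading.

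**Step 4. Is there an order of precedence?** The pointers in 6.1.1 and 6.1.2 send the reader to Section 6.3.1 and Table 6-4, but neither says that the table overrides the Grade 3 sentence.

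**Step 5. How many patients could be affected?** Inputs are from the Amendment 05 study status.

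- Treated: 60 + 81 = 141. On treatment at 08-Jul-2019: 6. Share: 6/141 = 4.3%.
- Infusions per 21-day cycle: 6 × 1 = 6 to 6 × 2 = 12, since the number receiving one or both antibodies is not stated.
- Last enrolment, 10-Jan-2019, to 08-Jul-2019: 21 + 28 + 31 + 30 + 31 + 30 + 8 = 179 days.
- Assuming a first dose 0 to 21 days after enrolment and no skipped doses, the last-enrolled patient, if among the 6, had been on treatment for 179 to 158 days. Scheduled dosing days so far: floor(158/21) + 1 = 8 to floor(179/21) + 1 = 9. The others would have had at least as many.
- Grade 3 anaphylactic reactions reported in the documents: none. No rate is given, so no expected count can be formed.

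**The case against.** The best reply is that the table row is headed with the clinical concept, not a CTCAE term. An infusion reaction described as anaphylaxis is still an infusion reaction, 6.1.2 sends infusion reactions to Table 6-4, and so discontinuation governs whatever the label. This is a fair reading, and it means the documents do not support saying that the coded term by itself switches the rule. It does not remove the conflict, however: the table then bars what the Grade 3 sentence conditionally permits for the same event. The sentence could be kept alive by confining it to reactions not caused by study drug, such as to CT contrast, but that is strained in a section about infusing the study antibodies.

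It is also true that the sentence is a restriction and not a right to re-treatment, and that a site obeys both texts by stopping. That stands, and it limits the point to re-exposure being left open. Other safeguards stand too. Sponsor discussion is required, Section 7.1.3 tells the investigator to stop when continuing would be detrimental, and dosing takes place with resuscitation equipment and a physician to hand.

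A reader might go further and infer a second route to re-exposure, in which an event recorded as allergic reaction or anaphylaxis, having no row of its own, falls to the Table 6-4 row headed "Other non-laboratory adverse events, not specified elsewhere in table and not included in the consensus guidelines". At Grade 3 that row requires a hold, after which "resuming study treatment must be discussed with the Novartis Medical Monitor". The documents do not establish this. The row applies only to events outside the consensus guidelines, and those guidelines are not available here. The 6.1.2 sentence names only anaphylactic and anaphylactoid reactions, so nothing else supports a separate point about allergic reactions.

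**Conclusion.** The two texts conflict for a Grade 3 anaphylactic reaction to a study infusion, and the protocol does not say which prevails. The conclusion rests on two readings: that anaphylaxis is one description of an infusion reaction, which 6.1.2 states, and that continuing on the study means continued dosing, which 7.1.3 and 6.3.1 support. It does not depend on the catch-all row or on how allergic reactions are handled. It also does not amount to a finding that the protocol requires or entitles anyone to re-exposure.

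The size is small. Six patients were on treatment at the last reported date, all in Phase II, and under the timing assumptions above each had at least 8 scheduled dosing days behind them. No such event is reported. The reason to correct it is that those patients were still being infused, and a stopping rule for a severe reaction should be unambiguous.

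**What to change.** In the next written amendment:

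1. In Section 6.1.2, replace the Grade 3 anaphylaxis sentence with a cross-reference to the Infusion Reaction, Grade 3 or 4, entry of Table 6-4.
2. In that entry, state that it applies to infusion reactions whichever CTCAE term is recorded, including anaphylaxis.
3. Leave the Grade 1 and Grade 2 entries unchanged.

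The stricter direction fits the protocol's existing pattern, since Grade 3 cytokine release syndrome, another term 6.1.2 allows for an infusion reaction, already leads to discontinuation.

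The cost is one sentence and one table entry, with the sponsor, ethics committee and, where required, health authority approvals set out in Section 12.1. The real downside is that the sponsor loses case-by-case discretion to re-expose a patient after Grade 3 anaphylaxis to a study infusion. If the sponsor wants to keep that discretion, it should be written into Table 6-4 so that the two texts still agree.

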6.1.3 Treatment duration

A patient may continue to receive study treatment until the patient experiences unacceptable toxicity, confirmed disease progression per irRC and/or treatment is discontinued at the discretion of the investigator or the patient. Patients will not be withdrawn from the study due to progressive disease per RECIST. In addition to safety and efficacy criteria, investigator’s opinion of the patients best interest and clinical benefit from treatment may be discussed on a case by case basis with Novartis. Refer to [Section 6.3.1](#), [Section 7.1.4](#) and [Section 7.1.6](#).

6.2 Dose escalation guidelines

6.2.1 Starting dose rationale

This is the first study evaluating the combination of MCS110 and PDR001. Potential overlapping toxicities include liver enzyme elevations caused by immune induction (PDR001) or reduced elimination of liver enzymes (MCS110), higher frequency or aggravation of immune mediated adverse events and skin toxicity.

The starting dose and regimen of MCS110 will be 3 mg/kg iv every 3 weeks, corresponding to approximately 40 % of the single agent dose administered in PVNS patients (10 mg/kg every 4 weeks in study [\[MCS110X2201\]](#)) and 30 % of the dose administered in combination with carboplatin/gemcitabine in TNBC (10 mg/kg every 3 weeks in study [\[MCS110Z2201\]](#)). An MCS110 dose of 10mg/kg was well tolerated in HV and PVNS patients ([\[CMCS110X2101\]](#) and [\[CMCS110X2201\]](#)) and showed significant tumor reduction in PVNS patients. After a single dose of 3 mg/kg of MCS110 in HV, it was observed that CSF-1 has been saturated by MCS110 for approximately 21 days [\[CMCS110X2101\]](#). PD analyses performed in HV studies indicate that circulating biomarker response should be close to maximal with dose at or above 5mg/kg and minimal with doses below 3 mg/kg. Considering the risk of potential overlapping

toxicities, the dose of 3 mg/kg MCS110 was selected as the starting dose for the dose escalation part of the study.

The starting dose and regimen of PDR001 will be 100 mg iv every 3 weeks. As of 30-Nov-2015, PDR001 has been tested up to the dose of 10 mg/kg every 2 weeks in the ongoing [CPDR001X2101] study. No MTD has been determined and the planned RP2D is 300 mg (3.75 mg/kg) given every 3 weeks or 400 mg (5 mg/kg) given every 4 weeks. Both of the proposed RP2Ds would be expected to achieve the steady mean C_{trough} concentrations that are approximately 77 fold higher than the in vitro/ex vivo potency EC50 for PDR001 assessed as 0.42 $\mu\text{g/mL}$. In addition, the expected PDR001 C_{trough} concentrations are in line with observed steady state mean C_{trough} concentrations for pembrolizumab whose ex vivo potency EC50 is approximately 0.4 $\mu\text{g/mL}$ utilizing the same assay. Pembrolizumab has been approved with substantial efficacy in several cancer types. The PDR001 exposure at a starting dose of 100 mg Q3W is within the range of those observed in the CPDR001X2101 study with no DLTs (section 1.2.1.2). PDR001 is expected to demonstrate antitumor activity at doses of 100 mg or above every 3 weeks. The starting dose is in accordance with clinical experience of nivolumab and pembrolizumab (Topalian 2012, Topalian 2014, Hamid 2013b, Robert 2014).

6.2.2 Provisional dose levels

Table 6-2 describes the starting dose and the dose levels that may be evaluated during this trial.

Table 6-2 Provisional dose levels

Dose level *	Proposed dose MCS110	Proposed dose PDR001
-2**	0.3 mg/kg Q3W	100 mg Q3W
-1**	1 mg/kg Q3W	100 mg Q3W
1 (starting dose)	3 mg/kg Q3W	100 mg Q3W
2	3 mg/kg Q3W	300 mg Q3W
3	5 mg/kg Q3W	300 mg Q3W
4	10 mg/kg Q3W	300 mg Q3W

* It is possible for additional and/or intermediate dose levels to be added during the course of the study. Cohorts may be added at any dose level below the MTD in order to better understand safety, PK or PD

** Dose level -1 or -2 represent provisional dose levels and/or treatment doses for patients requiring a dose reduction from the starting dose level. No dose reduction below dose level -2 is permitted for this study

6.2.3 Guidelines for dose escalation and determination of MTD or RP2D

The maximum tolerated dose (MTD) is defined as the highest combination drug that is unlikely (< 25% posterior probability) to cause DLT in 33% or more of the treated patients in the **first two cycles (42 days)** of treatment.

The applied adaptive Bayesian methodology provides an estimate of the combinations of MCS110 and PDR001 not exceeding the MTD. Typically the MTD is a tested combination with maximum probability of targeted toxicity (DLT rate between 16% and < 33%). The use of the EWOC principle limits the risk that a potential next dose will exceed the MTD (Section 10.4.2). Adverse events and laboratory abnormalities considered to be DLTs are defined in Table 6-3.

For the purposes of dose escalation decisions, each cohort will consist of 3 to 6 newly enrolled patients who will be treated at the specified dose level. The first cohort will be treated with the starting doses of 3 mg/kg MCS110 Q3W and 100 mg PDR001 Q3W.

Patients must complete a minimum of two cycles of treatment with the minimum safety evaluation and drug exposure or have had a DLT within the first two cycles of treatment to be considered evaluable for dose escalation decisions ([Section 10.1.4](#)). Dose escalation decisions will occur when the cohort of patients has met these criteria. If only 2 of the 3 patients in a cohort are evaluable and neither subject has experienced a treatment-related toxicity > CTCAE Grade 1, dose escalation decisions may be considered.

Dose escalation decisions will be made by Investigators and Novartis study personnel. Decisions will be based on a synthesis of all relevant data available from all dose levels evaluated in the ongoing study including safety information, DLTs, all CTCAE Grade ≥ 2 toxicity data during Cycle 1 and 2, PK, and PD data from evaluable patients. The recommended dose for the next cohort of subjects will be guided by the BLRM with EWOC principle evaluating the probability of DLT ([Section 10.4.2](#))

The adaptive Bayesian methodology provides an estimate of all dose levels of the combination MCS110/PDR001 that do not exceed the MTD and incorporates all DLT information at all dose levels for this estimation. In general, the next dose will have the highest chance that the DLT rate will fall in the target interval [16-33%) and will always satisfy the EWOC principle (less than 25% probability that the DLT rate is $\geq 33\%$). In all cases, the dose for the next cohort will not exceed a 100% increase from the previous dose (except for the first dose escalation step where MCS110 remains at 3 mg/kg, while PDR001 is allowed to have a 200% increase from 100 mg). Smaller increases in dose may be recommended by the Investigators and Sponsor upon consideration of all of the available clinical data.

If 2 patients in a previously untested dose level experience a DLT, enrollment to that cohort will stop, the BLRM will be updated and the next cohort will be opened at the next lower dose level or an intermediate dose level (see [Table 6-2](#) for provisional dose levels and [Appendix 3](#)) that satisfies the EWOC criteria. However, if 2 patients in a new cohort at a previously tested dose level experience a DLT (e.g., a total of 8 patients are treated on this dose level with 2 DLTs observed), further enrollment to that cohort will stop, the BLRM will be updated with this new information and re-evaluation of the available safety, PK, and PD data will occur. By incorporating information gained at the preceding dose cohorts, additional patients may be enrolled into the current dose level or a lower dose level as agreed by Investigators and Novartis personnel and if the BLRM predicts that the risk for this dose to exceed the MTD(s) remains below 25% (EWOC). Re-escalation may then occur if data in subsequent cohorts supports this EWOC criteria are satisfied and Investigators and Novartis personnel agree

Dose escalation will continue until identification of the RP2D which is expected to occur before the MTD is reached. This will occur when the following conditions are met:

1. at least 6 patients have been treated at this dose
2. this dose satisfies one of the following conditions:
 - a. the posterior probability of targeted toxicity at this dose exceeds 50% and is the highest among potential doses, or

- b. minimum of 15 patients have already been treated on the trial to identify the MTD. Recommendation of RP2D may be made with fewer patients, without identification of MTD.
3. it is the dose recommended for patients, either per the model or by review of all clinical data by Novartis and Investigators in a dose-escalation teleconference, see [Section 6.2.3.1](#).

To better understand the safety, tolerability and PK of both MCS110 and PDR001, additional cohorts of patients may be enrolled at preceding dose levels, or to intermediate dose levels before or while proceeding with further dose escalation.

If a decision is made to escalate to a higher dose level but one or more additional patient(s) treated at the preceding dose level experiences a DLT during the first two cycles of treatment, then the BLRM will be updated with this new information before any additional patients are enrolled at that higher dose level. Subjects ongoing will continue treatment at their assigned dose levels.

